Once eligibility is confirmed, subjects will be approached to obtain their authorization to access and use their health information for the research. Please see Section 14 for additional information regarding Data Management and Confidentiality.

8) Compensation to the Subjects

Subjects will not be compensated for their participation. Possible expenses to the subject's family include time spent at the clinic as well as expenses for travelling. Therefore subjects who would otherwise not be able to participate may be eligible for travel reimbursement for travel costs incurred as specified in question 25.

9) Study Timelines

We anticipate seeing 30 pilot participants in the first 18 months under consent form C. During this same time period up to an additional thirty participants and their mothers will be seen under consent form A, phases 1 and 2 of the study. During Phase 3, 50 participants and their parent/caregiver will be recruited into the clinical trial portion utilizing consent form B. In addition, 3 subjects will be recruited into phase 4, under consent form D. Phases 2,3, and 4 of the study, using consent forms A, B and D, will occur over the last 3.5 years of the project).

10) Study Endpoints

The primary outcome measure is a spoken language composite measured at baseline and at the end of treatment. Comparison of the two treatment groups on the outcome measure will be made through analysis of covariance, adjusted for baseline values on that measure using an intent-to-treat approach. Two-sided tests will be used with alpha at .05. With this sample size, power to detect a moderate effect size of 0.6 will be 80%, assuming equal standard deviations in the groups. The assumptions we are making to estimate power are conservative as evidenced by recent published tests of a parent mediated intervention for autism (Rogers et al., 2012) and a randomized controlled trial of a drug in FXS (Berry-Kravis et al., 2012), with samples sizes of 98 and 60, respectively, and behavioral outcome measures.

Analysis of our secondary outcome measure, the social avoidance subscale of the FXS- normed ABC, as well as the exploratory VAS and CGI will follow the same approach as the primary analysis. Additional analyses will examine potential child moderators of response to lovastatin (age, Leiter, ADOS symptom severity) using linear regression.

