ix. Child Spoken Language: ICF A and B

The conversation and narration procedures described in Preliminary Studies will be administered at the baseline and post-treatment visits. Alternate versions of conversation and narration materials will be administered at the two visits and counterbalanced.

Neurobehavioral Analysis Core staff blind to hypotheses and participant characteristics will transcribe/code. A spoken language ability composite will be obtained for each assessment time by taking a weighted mean of variables reflecting talkativeness, fluency, intelligibility, vocabulary diversity, and syntactic complexity in combined narrative and conversational samples. This composite will provide a broad-based and robust measure of spoken language ability and serve as the primary outcome measure. Exploratory analyses will evaluate the separate contributions of the variables included in the composite (30 min).

DOS 5.1 (Version Date: 07-Nov-2017)

x. The Social Communication Questionnaire (SCQ): ICF D

A widely used informant report checklist that evaluates communication and social skill deficits common to those with symptoms of autism. This brief questionnaire will be completed by the participant's parent/caregiver (10 min).

xi. The Vineland Adaptive Behavior Scales (VABS): ICF D

The VABS is a widely used informant report checklist that will be used to assess four domains: communication; self-care; social skills; and maladaptive behavior. It will be completed by the participant's parent/caregiver (30 min).

xii. Childhood Autism Rating Scale, Second Edition (CARS-2): ICF D

An examiner completed behavioral rating scale used to evaluate symptoms of autism following a direct observation of a child. The parent-child structured interaction will be used as the context which is evaluated for this measure.

xiii. The Aberrant Behavior Checklist (ABC): ICF A, B, and D

A behavior rating scale completed by the parent/caregiver that is frequently used to examine treatment effects on challenging behaviors for individuals with FXS. The scale is comprised of 58-items in the following domains: (1) irritability, agitation, crying; (2) lethargy, social withdrawal; (3) stereotypic behavior (4) hyperactivity, noncompliance; and (5) inappropriate speech (15 min). The Sansone et al. (2011) FXS-normed ABC scoring measures will be used. The social avoidance subscale score will be a secondary clinical endpoint.

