Parent use of targeted intervention strategies and child spoken language will be assessed during joint book reading within two contexts at both the pre- and post-treatment assessment. The contexts will be 1) at the clinic visit, and 2) in the family home via distance teleconferencing. The parent/caregiver and child will look at a wordless picture book together and the parent/caregiver will be instructed to look at each page of the book and tell the story with his/her child as he/she usually would. A set of two wordless picture books will be used in each sampling context and the books will be randomly assigned to participants and counterbalanced at the pre- and post-assessment time points. The following parent and child variables will be obtained from each context and average to create composite variables. Parent variables: story-related talking, open-ended questions, use of expansions, use of intonation prompts. Child variables include: Mean length of utterances, number of different words, story-related talking, intelligibility, mazes, off-topic utterances, and repetitive utterances. Each sample will last approximately 15 minutes.

i. Parent/Child Narrative Task 1(Clinic): ICF A and B

The parent/caregiver will tell a story with the child using the wordless picture books *Frog Where are You* (version A) or *One Frog Too Many* (version B). The parent/caregiver will be encouraged to look through/familiarize themselves with the book in advance of the language sampling session (15).

min, Pre/Post Consent Form Versions A and B).

ii. Parent/Child Narrative Task 2 (Home): ICF A, B, and D

Parent/caregiver will tell a story from a wordless picture book from a selection of books that will not be used during the intervention. The parent/caregiver will be encouraged to look through/familiarize themselves with the book in advance of the language sampling session.).

iii. Parent/child structured interaction - Child: ICF D

The parent will interact with the child during four activities: joint book reading, preparation of a snack, completion of a goal-directed construction activity, and free play. The mother will be instructed to participate and involve the child as much as possible. Sessions will be coded to determine maternal use of responsive verbal interaction strategies, child spontaneous and prompted communication acts, and child challenging behaviors (20 min).

The following are exploratory measures:

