Randomization to lovastatin or placebo will be conducted by the UCDMC pharmacy using a computer algorithm. IDS will over-encapsulate the active study medications and prepare the placebo capsules prior to dispensing. Equivalence of the groups on these stratification variables, as well as other variables (e.g., child autism symptom severity and maternal IQ), will be tested, with any significant differences accounted for by inclusion of covariates in the primary analyses.

The dose will range from 10 to 40 mg of lovastatin or placebo depending on tolerance of the dose. The dose will start at 10 mg per day and will be increased by 10 mg increments on a weekly basis from study weeks 1 through 4 as listed below. Dosing will occur once per day in the evening. Dose tolerance will be assessed through a weekly phone call or email contact conducted by a study physician during the titration period and a dose decrease can be made if necessary. If a dose decrease is made between weeks 2 and 4 no further dose titrations will occur and subject will be considered on a stable dose throughout the remainder of the titration period and study.

If more than one dose change is needed, the subject will be discontinued from the study. Once a stable dose is reached, subjects will remain at the designated dose through visit 3 and will be contacted approximately every other week by study staff to assess for possible adverse events and verification of proper dosing. Study participants will be dispensed study medication at visits one and two and will discontinue dosing after completing visit 3.

Week 1: 10 mg (Day 1-7) Week 2: 20 mg (Day 8-14) Week 3: 30 mg (Day 15-21) Week 4: 40 mg (Day 22- 28) Week 5-20: 40 mg or OTD (Day 29- 140)

Our dosage model takes into consideration the biphasic and pleiotropic effects of statins. The biphasic effect can be explained by the higher affinity for the enzymes that catalyze non-sterol product formation than for the cholesterol biosynthesis enzymes. Low doses of statins mainly affect cholesterol synthesis, while high doses affect mevalonate-derivative intermediates, which are essential for the prenylation of proteins and Ras activation (Li, et al., 2007). The pleiotropic effects of statins suggest that the sustained use of statins (more than 2 weeks) causes PTEN up regulation, which inhibits the PIK3/AKT pathway; and that higher acute dose administration of statins will inhibit Ras, which is our targeted effect. (Ludman, et al., 2009).

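### The primary ANCOVA omits the counterbalanced version order, so any difference between test versions costs some precision on the spoken language composite

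*Combined protocol and SAP*

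**What the plan says.** Section 10 defines the endpoint: "The primary outcome measure is a spoken language composite measured at baseline and at the end of treatment". It then gives the model: "Comparison of the two treatment groups on the outcome measure will be made through analysis of covariance, adjusted for baseline values on that measure". No other term is named there.

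Section 11(a), item ix (Child Spoken Language), describes how the composite is collected: "Alternate versions of conversation and narration materials will be administered at the two visits and counterbalanced". It does not say whether the conversation and narration materials follow one common order, or whether order is balanced within treatment arm.

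The only other route for a covariate into the primary model is in Section 11(b), after the schedule of procedures. The arms are to be compared on stratification and other variables, "with any significant differences accounted for by inclusion of covariates in the primary analyses". Version order is not mentioned, and the stratification variables are not named in that section.

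The parent-child narrative measures have a similar design in Section 11(a): "the books will be randomly assigned to participants and counterbalanced at the pre- and post-assessment time points". Section 10 does not put book order in the Hypothesis 1b regressions either.

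**The concern.** Counterbalancing stops version from being confounded with visit. It does not remove version differences from individual scores. Suppose version A elicits more language than version B. A child tested A then B is raised at baseline and lowered at Week 20, and a child tested B then A is shifted the other way.

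Adjusting for baseline might be expected to absorb this, but it works in the wrong direction. The model sees a high baseline, predicts a high Week 20 score, and meets a lowered one. The gap between the two orders in the adjusted outcome is therefore larger than the version difference itself.

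The trial sets the order and knows it for every child. Leaving it out of the model puts explainable variation into the error term of the primary test, in a trial of 50.

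**Working it through.** **Inputs from the documents.** Up to 50 children in the clinical trial (Section 6), half randomised to lovastatin (Section 17), so 25 per arm. On the test, Section 10 says: "Two-sided tests will be used with alpha at .05". On power, it says "power to detect a moderate effect size of 0.6 will be 80" per cent. No SD is given, so the within-version SD is set to 1.

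**Assumptions.** The documents give neither the baseline to Week 20 correlation r nor the version difference δ (in SD). The range for δ is 0 to 0.5. Dropout is taken as zero.

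**Step 1: the plan's own power figure.** Without baseline adjustment, SE = √(2/25) = 0.283 and 0.6/0.283 = 2.12. Power is then 54.7% (t test), and 80% would need 44 per arm. With baseline adjustment the residual variance is 1 − r². At r = 0.67 it is 1 − 0.449 = 0.551, so SE = √(0.551 × 2/25) = 0.210, 0.6/0.210 = 2.86, and power is 79.9%. The plan does not state r = 0.67. It is used below because it is the value at which the stated 80% comes out.

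**Step 2: what order does to the residual.** Code order as o = ±1.

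- Baseline = u1 + oδ/2.
- Week 20 = u2 + effect × arm − oδ/2.
- Baseline slope with order omitted: b = (r − δ²/4)/(1 + δ²/4).
- Gap between orders in the adjusted outcome: δ(1 + b).
- Residual variance without order: V = (1 + δ²/4) − (r − δ²/4)²/(1 + δ²/4).
- Residual variance with order: 1 − r².

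At δ = 0.5, δ²/4 = 0.0625. Then b = 0.6075/1.0625 = 0.572, the gap is 0.5 × 1.572 = 0.79 SD, and V = 1.0625 − 0.6075²/1.0625 = 0.715. Against 0.551, that is 30% more residual variance.

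**Step 3: power without and with order (r = 0.67, effect 0.6, 25 per arm).** The formula uses 47 and 46 error degrees of freedom. The simulation leaves order unrelated to arm. Its ranges span repeated runs, rounded.

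| δ (SD) | V without order | Increase | Formula: without / with | Simulation: without / with |
|---|---|---|---|---|
| 0 | 0.551 | 0% | 79.9% / 79.9% | 78–79% / 77–78% |
| 0.1 | 0.558 | 1.3% | 79.4% / 79.9% | 79% / 78% |
| 0.2 | 0.579 | 5.0% | 78.0% / 79.9% | 76–78% / 78–79% |
| 0.3 | 0.613 | 11% | 75.6% / 79.9% | 75–76% / 78–79% |
| 0.5 | 0.715 | 30% | 69.0% / 79.9% | 68–69% / 78–79% |

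The simulated figures are slightly lower because the formula ignores chance imbalance of baseline and order between arms. That is also why the extra term costs up to about 1 point when the versions are equal, and why it gains nothing up to about 0.15 SD.

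**Step 4: validity.** At δ = 0.5 with order unrelated to arm, the mean reported SE is 0.241 without order and 0.213 with it. Type I error is about 5% both ways, and the simulated treatment effects average 0.60 in both models. If order is balanced within arm but omitted, the reported SE is still 0.241 while the true sampling SD is 0.216. Type I error then falls to about 3%, and power is about 70% against 79% with order in the model.

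**Step 5: other correlations (formula, effect 0.6).** At r = 0.5, power goes from 65.7% to 66.9% at δ = 0.2 and from 60.0% to 66.9% at δ = 0.5. At r = 0.8, it goes from 91.3% to 93.3% and from 80.0% to 93.3%.

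**The case against.** The strongest reply is that the size is assumed. The composite is a weighted mean of five features over combined conversation and narration samples. A shift of 0.5 SD would need the versions to differ in the same direction across most of it, and nothing in the documents suggests that. At 0.1 SD or less the extra term gains nothing. This stands, and it limits the point to a low-cost safeguard.

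Two stronger readings are tempting. One is that omitting order biases the treatment estimate or makes its error bars unreliable. The documents do not support this. When order is unrelated to arm, chance imbalance is ordinary random error that the standard error already reflects. The reported error is too large only if order is balanced within arm, which the text does not state, and even then the test is conservative. The other is that the omission disproves the stated 80% power. It does not: that figure depends on an unstated baseline correlation, which is a separate matter.

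The covariate rule in Section 11(b) might seem to cover the point already. It acts only on significant differences between arms, and a counterbalanced factor would rarely show one. The harm here also does not require any difference between arms.

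Lastly, version details may lie in the preliminary studies that item ix refers to, which are not part of this text. One common order for conversation and narration therefore cannot be taken for granted.

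**Conclusion.** The omission is clear in the text, and the mechanism follows by algebra. The consequence is a loss of precision whose size the documents do not allow one to fix. At r = 0.67 and an effect of 0.6 SD, adding order changes power by about −1 point if the versions are equivalent. The gain is about 1 point at a version difference of 0.2 SD, 3 to 4 points at 0.3 SD and about 10 points at 0.5 SD. Confidence is high that order is missing from the model, and low on how much that matters here. It is worth changing because order is a known design factor and the change costs almost nothing, not because the planned test is invalid. Label: cheap improvement.

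**What to change.** **Section 10.** State that the primary ANCOVA includes treatment arm, the baseline composite and version order as a fixed two-level factor, kept whatever its p-value. If conversation and narration are counterbalanced separately, include one factor for each. Section 11(a), item ix, should say which applies, and the version given at each visit should be recorded for every child.

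**Cost.** One sentence, no new data, and one error degree of freedom per factor (47 to 46, or 45 with two factors). If the versions prove equivalent, one such factor costs about 1 point of power or less. The term should be fixed before unblinding, since adding it later would look data-driven.

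**Balance within arm (optional).** Baseline language sampling belongs to the screening/baseline visit, and Section 28 places randomisation after screening evaluations are complete. As the text reads, the baseline version has been used before the arm is known. Balance within arm would therefore need order as a randomisation stratum. Once order is in the model this adds little.

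**Hypothesis 1b.** The same adjustment can be made for book order in the parent-child narrative measures. It should be done by context, because clinic and home each have their own pair of books and the two are averaged.

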- 3. Changes in behavioral therapy or educational programming during the study. This does not include scheduled school holidays.
- 4. Have any disease or condition (medical or surgical) at screening that might compromise the hematologic, cardiovascular, pulmonary, renal, gastrointestinal, or hepatic systems; or other conditions that might interfere with the absorption, distribution, metabolism, or excretion of the investigational product, or would place the subject at increased risk.
- 5. Patients who, in the opinion of the investigator, are unsuitable in any other way to participate in this study, including being unable to comply with the requirements of the study or displaying clinically significant abnormalities in safety assessments at screening.
- 6. Patients on prohibited medications (see package insert for more information):
 - a. Potent inhibitors of CYP3A4 (itraconazole, ketoconazole, posaconazole, voriconazole, HIV protease inhibitors, boceprevir, telaprevir, erythromycin, clarithromycin, telithromycin, and nefazodone)
 - b. Gemfibrozil
 - c. Other lipid-lowering drugs
 - d. Cyclosporine
 - e. Danazol, diltiazem, dronedarone, or verapamil
 - f. Amiodarone
 - g. Colchicine
 - h. Ranolazine
 - *i.* Coumarin anticoagulants
 - j. mGluR5 antagonists
- 7. History of recurrent status epilepticus.
- 8. Inability to withhold grapefruit and grapefruit juice from diet during the entire clinical trial.

- 9. Subjects unwilling to abstain from alcoholic beverages during the trial
- 10. Subjects who are actively suicidal.

6) Number of Subjects

We hope to enroll up to 113 participants through the entire study under the 4 consent form versions. Consent form A will be utilized to enroll up to 30 subjects and their mothers. Consent form B will be utilized to enroll up to 50 subjects and their mothers/caregivers into the clinical trial portion of the study. Up to 30 additional pilot participants may be recruited from ongoing studies here at the MIND using Consent form C. Mothers of the pilot participants enrolled under consent form C will not be involved in the clinician-child interactions. We will also recruit 3 boys with FXS between the ages of 5- and 8-years old to participate in a downward extension of the study utilizing Consent form D. This brings the total number of potential participants to 113.

7) Recruitment Methods

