on their observations of the parent/child interaction. Finally, the parent/caregiver and child will participate in one additional book sharing activity during each week which will serve as the context for data collection. Intervention targets will be individualized. Language goals for the child will be selected based on the results of the baseline spoken language sampling procedures. PVR targets for the parent/caregiver will be selected based on results of the baseline shared storytelling and structured interaction procedures. Child challenging behavior goals will be selected based on the results of the baseline Functional Behavior Assessment. The SLP and BCBA will coordinate their planning to ensure that targets and procedures form a consistent and coherent plan. As is customary in PILI, the parent/caregiver will be involved in prioritizing targets.

Child Assessment Measures

The following measures will be used to verify that participants meet screening criteria, verify that random assignment has yielded equivalent groups, and provide variables that can be examined as potential moderators of treatment response. To ensure accurate scoring and for study training purposes some assessments may be audio and/or video recorded at the pre and post visits. Any assessments or study procedures deemed not appropriate for a subject based on their cognitive abilities and behaviors will not be completed with the exception of those required for inclusion/exclusion criteria and safety assessments.

- i. Clinical Evaluation of Language Fundamentals 4 (CELF-4): ICF A and B A standardized norm- referenced assessment that provides subtests assessing sentence comprehension, following directions, formulated sentences, and written language (15 min).
- ii. Leiter International Performance Scales: ICF A and B

 A published, standardized, norm-referenced test designed to measure developmental functioning and IQ for individuals ranging in age from 2 years to adulthood. Minimal verbal directions are used in the administration to allow assessment of cognitive ability independent of language ability. The tasks require matching shapes, completing visual sequences through card placements, and detecting sequences and component parts. The figure ground, form completion, sequential order, and repeated patterns subtests will be administered to determine Brief IQ (45 min).
- iii. Comprehensive Assessment of Spoken Language (CASL): ICF A and B

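### Apart from the baseline composite, covariates enter the primary ANCOVA only after a significant baseline test over an open list, and the stratification variables are unnamed with no fixed place in the model.

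*Combined protocol and SAP*

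**What the plan says.** Section 10 (Study Endpoints) sets the primary analysis: "Comparison of the two treatment groups on the outcome measure will be made through analysis of covariance, adjusted for baseline values on that measure". It adds "Two-sided tests will be used with alpha at .05" and claims "power to detect a moderate effect size of 0.6 will be 80%, assuming equal standard deviations in the groups". No other covariate is fixed for this model. Age, Leiter and ADOS severity appear in section 10 only as moderators in additional analyses, and the SCL-90-R only in the Hypothesis 1b regression.

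The randomization paragraph of section 11(b) supplies the rest. "Equivalence of the groups on these stratification variables" is to be tested along with other variables, of which child autism severity and maternal IQ are given as examples, "with any significant differences accounted for by inclusion of covariates in the primary analyses". The paragraph describes randomization only as a pharmacy computer algorithm. Neither it nor section 28 (Drugs or Devices) names a stratification factor.

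Section 11(a), Child Assessment Measures, says the listed measures will be used, among other purposes, to "verify that random assignment has yielded equivalent groups".

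**The concern.** Under randomization, a significant baseline difference is a chance event. It does not show that the variable predicts outcome, which is the reason to adjust for it. The rule works worst for stratification factors: stratifying balances them, so the test almost never selects them. If they predict outcome and are omitted, the standard error is too large for the design, the test becomes conservative and power falls.

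The primary model also cannot be written down until the arms have been compared. The list of variables is open, and no threshold is tied to the baseline tests. Section 10 says the secondary, VAS and CGI analyses follow the primary approach, so the ambiguity may carry over to them. With only 50 participants, several points of power matter.

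**Working it through.** **Inputs from the documents.** Section 6: "Consent form B will be utilized to enroll up to 50 subjects and their mothers/caregivers into the clinical trial portion of the study". Section 17 says half receive lovastatin, taken here as 25 per arm. Section 10 gives effect 0.6, two-sided alpha 0.05 and the baseline composite as covariate.

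**Assumptions (the documents give no figures).** Baseline-outcome correlation 0.5; baseline tests flagged at p < 0.05; R², the share of post-baseline outcome variance explained by the added terms, varied from 0 to 0.4.

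**1. The plan's own power figure.** Without adjustment, Φ(0.6 × √(25/2) − 1.96) = Φ(2.121 − 1.96) = 56.4%, or 54.7% by noncentral t, not 80%. ANCOVA on baseline reaches 80% only at a baseline correlation of about 0.65 (normal) or 0.67 (t). At 0.5 it gives 68.8% or 67.0%. This is a separate matter, but it shows how far the design depends on covariate adjustment.

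**2. How many variables the rule could test.** Twelve child measures in section 11(a) are marked for consent form B: CELF-4, Leiter, CASL, TROG-2, PPVT-4, EVT-2, ADOS-2, FACB, Child Spoken Language, ABC, RBS-R and ADAMS. Removing Child Spoken Language, the source of the composite, leaves 11; adding maternal IQ gives about 12. For independent tests, the chance of at least one flag is 1 − 0.95¹² = 46%. In simulation (6,000 trials per setting) it was 46%, 40% and 28% at inter-correlation 0, 0.3 and 0.6. Type I error under the rule was 4.0% to 5.3%, so no inflation was seen.

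**3. Omitting a balanced factor.** The estimate varies as if the factor were removed, but the model's standard error still contains it. The test statistic under the null therefore has standard deviation of about √(1 − R²), and type I error is about P(|Z| > 1.96/√(1 − R²)):

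- R² 0.1: 1.96/0.949 = 2.07, giving 3.9%
- R² 0.2: 1.96/0.894 = 2.19, giving 2.8%
- R² 0.4: 1.96/0.775 = 2.53, giving 1.1%

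**4. Simulation: two binary factors, stratified in blocks of 4 (8,000 trials per setting).**

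| R² | Type I error, rule | Type I error, fixed | Power, rule | Power, fixed |
|---|---|---|---|---|
| 0 | 5.0% | 5.1% | 65.1% | 65.2% |
| 0.1 | 3.9% | 4.8% | 65.5% | 69.3% |
| 0.2 | 3.0% | 4.9% | 65.8% | 74.9% |
| 0.4 | 1.4% | 5.0% | 68.8% | 86.4% |

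The type I errors under the rule agree with step 3. Across the simulations a stratified factor was flagged in 0 of 144,000 stratified trials. A separately written repeat (4,000 trials per setting) gave power of 68% against 76% at R² 0.2.

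**5. The proposed model: two factors plus two continuous covariates, R² split equally between them.**

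| Total R² | Stratified: power, rule | Stratified: power, fixed | Unstratified: power, rule | Unstratified: power, fixed |
|---|---|---|---|---|
| 0 | 65.1% | 63.2% | 65.0% | 62.0% |
| 0.1 | 65.2% | 67.7% | 65.1% | 66.3% |
| 0.2 | 66.4% | 74.4% | 66.4% | 72.0% |

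Fixed minus rule is −1.9, +2.5 and +8.0 points if stratified, and −3.0, +1.2 and +5.6 if not. Type I error of the fixed model was 4.6% to 4.9%.

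**The case against.** The strongest reply is that no bias or excess of false positives is shown. The rule uses baseline data only, so a chance flag merely adds a covariate that may do nothing. That is right: the flag rate in step 2 shows how often the model would change, not harm in itself.

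Second, the gain depends on R² after the baseline composite, and the same outcome measured at baseline already takes up much of what is predictable. With two covariates correlated 0.5 with baseline, 0.3 to 0.4 with outcome and 0.3 to 0.5 with each other, post-baseline R² is only about 0.01 to 0.08. At R² 0.02 to 0.05, fixing the two factors gains about 0 to 1 point, within simulation error. This stands as a limit on size, and R² 0.4 should be read as an extreme case.

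Third, it is not known that stratification was used. If it was not, the conservative-test argument largely falls away (type I error 4.0% to 4.9% in the unstratified four-term runs). Some pages were removed from the public document, so the factors can be called unnamed only in the available text.

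Fourth, the count of 12 is a reading of section 11(a). The section gives the measures several joint purposes, and the FACB mainly serves the behavior plan. Power was not simulated with 12 candidates. Finally, 0.05 is the only alpha stated, but section 10 does not tie it to the baseline tests.

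These points limit the size of the effect. None changes the text: entry still depends on a significance test over a list introduced by examples, and naming the factors elsewhere would not give them a fixed place in the model.

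**Conclusion.** The concern holds. The plan states a covariate rule for its primary model that selects on the wrong criterion, practically never admits stratification factors and leaves the candidate list open.

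The consequence is possible loss of power and a conservative test, not excess false positives. If stratification was used and two factors explain 20% of post-baseline variance, the loss is about 9 points (74.9% − 65.8%). At 10% it is about 4 points, and at 0 there is none. These figures rest on an assumed baseline correlation of 0.5, assumed R² values and an assumed flag threshold of 0.05. The flaw in the rule does not depend on them. The change should be made, with medium confidence about how much it gains.

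**What to change.** Replace the sentence on equivalence testing in the randomization paragraph of section 11(b), and repeat the new text in section 10:

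> The primary ANCOVA includes treatment, the baseline composite and the randomization stratification factors (named here, if any were used), plus a short closed list of prespecified prognostic covariates collected at baseline, regardless of observed balance. Baseline characteristics are described by arm without significance tests.

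Keep the list to about two covariates and fix it before unblinding. Leiter IQ and ADOS-2 severity are examples. The choice should be argued on expected prognostic value: age is listed beside them as a moderator, and the IQ ceiling at entry may weaken Leiter as a predictor. Section 11(b) names maternal IQ, so either include it or expressly leave it out. If there was no stratification, say so and delete the reference.

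No new data are needed: the schedule of procedures already has Leiter-R, ADOS-2 and maternal K-BIT-2 at baseline. Residual degrees of freedom are now 50 − 3 = 47; four added terms leave 43. The cost is about 2 to 3 points of power if those terms explain nothing.
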